9.5.3 Pre-medication

Pre-medication data (Paracetamol and antihistamine administration details) will be listed separately along with the verbatim and preferred drug name and WHO ATC Class (ATC Level 2) for all SAF subjects.

9.5.4 Prophylactic Hydration

Prophylactic hydration data will be listed for all SAF subjects.

9.6 Study Treatment Exposure and Compliance

Administration of intratumoral CyPep-1 and administration of IV pembrolizumab will be done in a hospitalized environment by trained trial personnel. Treatment compliance will be accomplished by documenting in record (i.e. the drug accountability, preparation, administration logs, the subjects' eCRF and medical records) information on, but not limited to: the batch number of CyPep-1 and of pembrolizumab used, the time point for preparation, the time point for administration, and signatures of designated site staff preparing and administering intratumoral CyPep-1 and pembrolizumab. Any deviations will be documented on the appropriate eCRF page.

9.6.1 CyPep-1

Exposure to and compliance with CyPep-1 will be summarized by cohort for the SAF by the following variables:

1. Number (%) of subjects exposed to CyPep-1 (overall and by cycle),
2. Number of CyPep-1 administrations (continuous variable),
3. Number (%) of subjects with one or more full dose of CyPep-1 not administered (overall and by cycle),
4. Number (%) of missed CyPep-1 administrations (overall; 0, 1, 2, 3, >3),
5. Number (%) of subjects with weekly CyPep-1 administration schedule during Cycle 1,
6. Average CyPep-1 dose per administration (continuous variable, see definition below),
7. Cumulative CyPep-1 dose (continuous variable, see definition below),
8. Average injected volume per administration (continuous variable, see definition below),
9. Cumulative injected volume (continuous variable, see definition below),
10. Number of injected lesions (overall; 1, 2, 3, 4, 5, >5),
11. Duration of treatment (continuous variable, defined in Section [8.4](#)),
12. Number (%) of times CyPep-1 not administered according to study protocol (overall; 0,1,2,3,>3).

A subject is counted as having been exposed to CyPep-1 in a cycle if the subject received CyPep-1 in given cycle.

Subjects with weekly CyPep-1 administration schedule during Cycle 1 are defined as subjects that received the first two doses of CyPep-1 within a 1-week interval.

For each subject, injected volume of CyPep-1 will be calculated for each administration of CyPep-1 as sum of injected volumes over all injected lesions. The CyPep-1 dose (mg) will be calculated as CyPep-1 concentration (mg/mL) multiplied with the injected volume of CyPep-1 (mL) for each administration of CyPep-1. An average injected volume will be calculated for each subject as mean of injected volume results of all CyPep-1 administrations and average dose will be calculated as mean of CyPep-1 dose results of all CyPep-1 administrations.

The cumulative dose (mg) will be calculated as sum of all doses received throughout the study. Cumulative injected volume (mL) will be calculated as sum of all injected volumes throughout the study.

CyPep-1 exposure and compliance data will be listed for all SAF subjects.

Statistical Analysis Plan

SMS-0571/CyPep-1

V3.0 Final

04-Jun-2024

Lesions targeted for injection (for all arms/cohorts) and lesion map information (for arm D only) will be listed for SAF.

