For Arm B, on the visits that CyPep-1 and pembrolizumab are administered on the same day, CyPep-1 is planned to be administered 30 to 60 min after pembrolizumab has been administered. In case of pembrolizumab-related toxicity, treatment with CyPep-1 will be delayed and planned after a review by the investigator and medical monitor. If CyPep-1 treatment is delayed > 7 days, that dose will be omitted. If the delay of > 7 days is during the TLT observation period, the subject will be replaced.

For Phase I, Phase IIa Arms A and C, CyPep-1 administration is planned as Q2W injections. If CyPep-1 treatment is delayed > 7 days, that dose will be omitted. If CyPep-1 treatment is delayed for > 6 weeks during the DLT period (first 3 injections), the subject should be discontinued from the trial.

For Arm D, CyPep-1 administration is planned as QW injections until the second iRECIST/itRECIST assessment at week 16, followed by a Q2W dosing scheme. In case CyPep-1 treatment is delayed for > 3 weeks (first 3 injections), the investigator and the Medical Monitor must assess on a case-by-case basis the decision whether the subject should be discontinued from the trial. Treatment delay due to TEAEs will be considered for treatment discontinuation.

Radiological assessment to determine occurrence of (un)confirmed PD will be performed Q8W from the start of treatment for all trial phases and arms. Treatment will continue until confirmed PD, unacceptable toxicity, death or consent withdrawal, loss to follow up, or trial end, whichever occurs first.

DOSE LIMITING TOXICITY:

A DLT is defined by the occurrence of any of the following toxicities according to CTCAE v5.0 during treatment Cycle 1 and that are considered by the investigator to be possibly, probably, or definitely related to CyPep-1:

1. Any Grade ≥ 3 AEs of any etiology, except:
 - Nausea, vomiting, or diarrhea will be considered a DLT only if it persists at Grade ≥ 3 for > 3 days despite adequate supportive care measures. At the investigator's

discretion, subjects who experience nausea, vomiting, or diarrhea after receiving CyPep-1 may receive antiemetic or anti-diarrheal medication prior to subsequent doses of CyPep-1.

- Isolated laboratory abnormalities Grade ≥ 3 (not present at baseline) that resolve to Grade ≤ 1 in ≤ 7 days without clinical sequelae or need for therapeutic intervention.
- Fatigue Grade ≥ 3 for ≤ 7 days.

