during or after IT administration, it is recommended to provide celecoxib 400 mg as premedication every 6 hours for 24-48 hours. Premedication should be administered for subsequent CyPep-1 doses based upon clinical judgment and presence/severity of prior reactions. This regimen may be modified based on local treatment standards and guidelines as appropriate. To ensure prophylactic hydration, subjects should consume ≥ 2 L of fluid intake per day, starting ≥ 48 hours prior to first dose/each dose escalation and for ≥ 24 hours thereafter. For subjects who have difficulty to maintain adequate oral hydration, intravenous hydration is recommended, at an infusion rate of 150-200 mL/hr (i.e., $2\text{-}3$ L per day) for initial dosing; for following dose escalations, an intravenous hydration with 1.5-2 L per day is advisable. For lesions > 7 cm, weekly CyPep-1 administration should be considered by the Investigator for the first 6 weeks, on Days 1, 8, 15, 22, 29 and 36 of cycle 1. The assessments are as per scheduled visit for Day 1, 15 and 29. Visits on Day 8 and 22 will follow the assessments as per D15 (C1V2) with the exclusion of central lab sampling for cytokine analysis and blood sampling for immune cell phenotyping. For Day 36 assessments as specified in the schedule need to be performed, with additional assessments: Pre-dose ECG, Vital Signs PRE- & 15m, 30m, 1h, 2h, 4h POST-dose, Coagulation and Pregnancy test (if applicable).

20. All concomitant medication/procedures should be reported beginning upon ICF signature until FU (or EoT, if it occurs more than 30 days after the last CyPep-1 or pembrolizumab administration).

21. Reporting period is from ICF signature until FU (or EoT, if it occurs more than 30 days after the last CyPep-1 or pembrolizumab administration). After the FU visit (or EoT, if it occurs more than 30 days after the last CyPep-1 or pembrolizumab administration), only ongoing (S)AEs related to CyPep-1 or pembrolizumab administration will be collected. Adverse events will be assessed using CTCAE v5.0 including start and stop dates, severity, relationship to CyPep-1 or pembrolizumab, outcome and action taken.

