For Phase IIa Arms A and B, for a lesion > 7 cm, the same lesion should be considered to be injected weekly with up to 4 mL of CyPep-1 for the first 6 weeks (on Day 1, 8, 15, 22, 29 and 36), independent of the potential change in lesion size, followed by Q2W 4 mL administrations of CyPep-1. The visits on Days 1, 15, 29 and 36 will follow the assessments as per schedule. The visits on Days 8 and 22 will follow the assessments as per D15 (C1V2; excluding central lab sampling for cytokine analysis and blood sampling for immune cell phenotyping).

For Phase IIa Arm D, the to-be-injected volume for injection is preferably divided over as many lesions as possible. The longest diameter of the lesions for injection is ideally smaller than 2 cm and should not exceed 5 cm.

For subjects in Arms A, B and C, the injection volume will be:

Measured Lesion Diameter (cm)	Injected volume (mL)
≤ 1	1
> 1 and ≤ 2	2
> 2	4

For subjects in Arm D, the injection volume will be:

Measured Lesion Diameter (cm)	Injected volume (mL)
≤ 0.79	0.1
0.80 to 0.99	0.2
1.00 to 1.24	0.5
1.25 to 1.50	1.5
1.51 to 2.49	3.0
≥ 2.50	4.0

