8.1.9 Exploratory Analyses

Exploratory analyses will be specified in the SAP. A separate analysis of subjects having received weekly vs Q2W CyPep-1 administration is planned as sub-group analysis.

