8.4 Relative Day (Study Day and Duration Variables)

Reference date calculations will generally be defined as the following, assuming non-missing dates:

*Date of interest – reference date + 1 when the date of interest >= reference date;
Otherwise, date of interest – reference date.*

Study day will either have a negative value if collected before dosing or a positive value if collected on or after the day of drug dosing; there will be no study day zero. In some cases, dates will be imputed (see Section 8.7) and reference date calculations performed on the imputed dates. If either date is missing (after imputation), reference date calculations will not be performed. In listings, only relative days calculated based on non-imputed dates will be presented.

Duration of time is dependent on reference dates and will be calculated in a manner similar to that of the reference date calculations.

Duration on study (months) is defined as:

(End of study date – informed consent date + 1) / 30.4375.

Duration of treatment (months) is defined as:

(Treatment end date – treatment start date + 1) / 30.4375.

Subjects still receiving ongoing treatment or participating in study follow-up at the time of analysis will use imputed end of treatment and end of study dates (see Section 8.7 for details). Duration of treatment will be calculated separately for CyPep-1 and pembrolizumab based on start and end dates of CyPep-1 and pembrolizumab, respectively.

Survival and time-to-event endpoints (e.g., PFS, OS) are followed until the first event or censoring. As a result, survival and time-to-event time (days) will be calculated as:

Event or censoring date – reference date + 1.

When reporting time-to-event data or duration outcomes, the results (in days) above will be converted to an appropriate unit. When reporting in months, it will be divided by 30.4375; for reporting in weeks it will be divided by 7; and for reporting in years it will be divided by 365.25.

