8.9 Multiple Assessments and Visit Windows

Nominal visits (i.e., those identified by the study eCRF) will be the basis of summarization and statistical analysis; no visit date windowing will be conducted. Unscheduled data may be included in summaries of most extreme and baseline; summaries of specific abnormalities any time post-baseline; summaries of tumor/response assessment data; and subject data listings.

For visit-based summaries, visit alignment (as described in [APPENDIX 4. VISIT ALIGNMENT](#)) will be used where appropriate to facilitate efficient reporting of data for arms with different visit schedules. Footnotes about visit alignment will be added to affected outputs. Visit alignment will only be used for tables; listings will present original (protocol planned) visit names.

Statistical Analysis Plan

SMS-0571/CyPep-1

V3.0 Final

04-Jun-2024

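### The SAP's weekly-dosing flag allows no timing tolerance, so a subject whose permitted Day 8 dose is given on Day 9 to 11 drops out of the Cycle 1 weekly count

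*SAP*

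**What the plan says.** SAP 9.6.1 lists among the CyPep-1 exposure summaries "Number (%) of subjects with weekly CyPep-1 administration schedule during Cycle 1". It then says that these subjects "are defined as subjects that received the first two doses of CyPep-1 within a 1-week interval". No tolerance is given. SAP 8.9 bases summaries on nominal eCRF visits and states that "no visit date windowing will be conducted". SAP 8.4 defines a relative day as the date of interest minus the reference date plus 1 (on or after the reference date) and adds: "Duration of time is dependent on reference dates and will be calculated in a manner similar to that of the reference date calculations".

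Protocol 5.3.1.2 asks that a lesion over 7 cm in Arms A and B be considered for injection "weekly with up to 4 mL of CyPep-1 for the first 6 weeks (on Day 1, 8, 15, 22, 29 and 36". Section 5.3.4 names Arms A, B and C for the same schedule; the two sections need to be reconciled. In the Schedule of Assessments, Table 1e gives ±3 days for Day 8 in Arm D. Tables 1a and 1c have no Day 8 column but give ±3 days for Day 15. Footnote 19 says for lesions over 7 cm: "Visits on Day 8 and 22 will follow the assessments as per D15 (C1V2". On late doses, the Synopsis (dose escalation and schedule) says for Phase I and Arms A, B and C: "If CyPep-1 treatment is delayed > 7 days, that dose will be omitted".

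On use of the schedule in analysis, protocol 8.1.9 says: "A separate analysis of subjects having received weekly vs Q2W CyPep-1 administration is planned as sub-group analysis". SAP 10.2.5 makes that comparison optional, subject to sufficient numbers in both groups, and plans none in this version.

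**The concern.** The flag is meant to identify which schedule a subject was on, but it tests how punctual the second dose was. An on-schedule weekly subject has a gap of exactly one week, so one day's lateness is enough to fail, although the protocol tolerates more than that.

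A weekly subject has six planned Cycle 1 doses (Days 1, 8, 15, 22, 29 and 36) against three on Q2W (Days 1, 15 and 29). The weekly count helps a reader interpret the number of administrations and the cumulative dose in the same table. If it is too low, those figures look like variation within one schedule. This is also the only definition of a weekly schedule in the SAP, so a later weekly versus Q2W comparison might well adopt it.

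**Working it through.** The plan states no figure to reproduce. The check enumerates calendar days.

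**Inputs.** First dose on Day 1. Weekly second dose on Day 8 ± 3, so Day 5 to Day 11 (Table 1e for Arm D; inferred from Day 15 through footnote 19 for Arms A and B). Q2W second dose on Day 15 ± 3, so Day 12 to Day 18 (Tables 1a and 1c). Flag rule: gap of at most 7 days (SAP 9.6.1).

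**Formulas.** Elapsed gap = second-dose day − 1. Under the SAP 8.4 convention, count = elapsed gap + 1.

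| Schedule | Second dose | Elapsed gap (days) | Count with +1 | Elapsed ≤ 7 | Count with +1 ≤ 7 | Elapsed ≤ 10 |
|---|---|---|---|---|---|---|
| Weekly, early | Day 5–7 | 4–6 | 5–7 | flagged | flagged | flagged |
| Weekly, on time | Day 8 | 7 | 8 | flagged | **missed** | flagged |
| Weekly, late in window | Day 9–11 | 8–10 | 9–11 | **missed** | **missed** | flagged |
| Weekly, delayed past window | Day 12–15 | 11–14 | 12–15 | missed | missed | missed |
| Q2W, in window | Day 12–18 | 11–17 | 12–18 | not flagged | not flagged | not flagged |

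**Result.** Read as elapsed days, the rule misses 3 of the 7 permitted days for the second weekly dose (Days 9, 10 and 11). With the add-one convention it misses 4 of 7, including the on-time Day 8. No in-window Q2W subject is ever flagged, so the error runs in one direction: undercounting weekly subjects.

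**Dependence on the inferred window.** For Arms A and B, footnote 19 transfers the Day 15 assessments and does not name the window. The delay rule gives a second route. A Day 8 dose delayed by up to 7 days falls no later than 8 + 7 = Day 15, so Days 9 to 11 lie inside that limit. That rule is written next to the Q2W schedule, so applying it to a Day 8 dose is itself a reading. Either route is enough.

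**Effect of a 10-day cut-off.** In-window weekly gaps are 4 to 10 days and in-window Q2W gaps are 11 to 17. A cut-off of 10 elapsed days separates these fully. It does not recover a Day 8 dose delayed to Day 12–15, whose gap of 11 to 14 days overlaps the Q2W range.

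**The case against.** The strongest reply is that little hangs on this flag. What it demonstrably feeds is one descriptive count. Exposure is listed for every subject in the safety set, and the number of administrations and cumulative dose are summarised, so extra Cycle 1 doses stay visible. That stands, and it sets the priority.

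Three stronger readings are tempting, and the documents do not support them:

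- A reader might infer that the flag defines the weekly versus Q2W comparison. Protocol 8.1.9 calls that comparison planned, but SAP 10.2.5 makes it optional, plans none in V3.0 and does not refer to the 9.6.1 definition.
- A reader might infer that missed subjects are classed as Q2W. SAP 9.6.1 has no Q2W category. The subject simply drops out of the weekly count into an unlabelled remainder.
- A reader might turn 3 of 7 days into a misclassification rate of 43%. That requires second doses to be spread evenly over the window, which nothing in the documents supports. The rate falls if doses cluster on Day 8.

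It can also be said that the ±3-day window is explicit for Day 8 only in Arm D, which stopped recruiting after one subject (SAP 6.1, footnote) and where weekly dosing follows from assignment to the arm. That is fair. For Arms A and B the point rests on the Day 15 window carrying over, or on the delay rule applying to the Day 8 dose.

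**Conclusion.** The mismatch is real and minor. Read as written, the 9.6.1 rule leaves a weekly subject out of the weekly count when the Day 8 dose is given on Day 9, 10 or 11, although the protocol permits that timing. Depending on how the interval is computed, it may also leave out a subject dosed exactly on Day 8. Nothing else in the SAP adds a tolerance.

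The number of subjects affected cannot be derived: the documents give neither the number on weekly dosing nor the actual dosing dates. Weekly dosing is something the investigator is asked to consider, so lesion size alone does not identify these subjects. No primary or secondary endpoint is touched. An effect on the weekly versus Q2W contrast is conditional on that analysis being run with this flag.

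**What to change.** Replace the definition in SAP 9.6.1. The more robust choice is to call a subject weekly in Cycle 1 if a CyPep-1 dose is recorded at the nominal C1 D8 visit. SAP Appendix 4 already lists that visit for Arms A, B and C, and SAP 8.9 already makes nominal visits the basis of summaries. The Appendix 4 entry carries an asterisk whose note was not in the text available to me, so it should be read first. Arm D uses DAY 8 in the same table.

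If a day count is kept, define weekly as 10 elapsed days or less between the first two administrations, computed as second-dose date minus first-dose date without adding 1. State the convention explicitly.

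Whichever key is chosen, name it in SAP 10.2.5 as the one to use if the weekly versus Q2W comparison is run.

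The cost is one sentence and one line of code before the final analysis, with no change to trial conduct. The day-count version still misses Day 8 doses delayed beyond Day 11. Neither version catches a weekly subject whose Day 8 dose was omitted altogether.

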9.6.2 Pembrolizumab

Exposure to and compliance with pembrolizumab will be summarized for combination arm B for the SAF by the following variables:

1. Number (%) of subjects exposed to pembrolizumab (overall and by cycle),
2. Number of pembrolizumab administrations (continuous variable),
3. Number (%) of subjects with one or more full dose of pembrolizumab not administered (overall and by cycle),
4. Number (%) of missed pembrolizumab administrations (overall; 0, 1, 2, 3, >3),
5. Average pembrolizumab dose per administration (continuous variable, see definition below),
6. Cumulative pembrolizumab dose (continuous variable, see definition below),
7. Duration of treatment (continuous variable, defined in Section [8.4](#)),
8. Number (%) of times pembrolizumab infusion temporarily interrupted or flow rate modified (overall; 0,1,2,3,>3),
9. Number (%) of times entire volume of pembrolizumab not administered (overall; 0,1,2,3,>3)
10. Number (%) of times pembrolizumab not administered according to study protocol (overall; 0,1,2,3,>3).

A subject is counted as having been exposed to pembrolizumab in a cycle if the subject received pembrolizumab in given cycle.

An average dose of pembrolizumab will be calculated as mean of pembrolizumab doses of all pembrolizumab administrations.

The cumulative dose (mg) will be calculated as sum of all doses received throughout the study.

Pembrolizumab exposure and compliance data will be listed for all SAF subjects in Arm B, including pembrolizumab infusion interruptions and modifications.

10 Efficacy Analysis

Antitumor activity will be assessed as a component of secondary and exploratory endpoints for this study. Evaluation of antitumor response will be based on investigator assessment of timepoint tumor response following iRECIST (for secondary and exploratory endpoints) and programmatically derived itRECIST (for exploratory endpoints for all Phase IIa arms).

iRECIST assessments will be based on CT scan or, if not available, on MRI, photograph (caliper), or ultrasound measurements, in this hierarchical order. In case any other method of evaluation is used, handling of such cases will be discussed separately with the Sponsor and documented appropriately. For comparability, all within-subject measurements need to be performed using the same method; this will be programmatically checked and potential deviations handled on a case-by-case basis⁴. Local measurements data will not be used for iRECIST assessments.

10.1 Secondary Efficacy Analyses

10.1.1 ORR in All Lesions (iRECIST)

A subject's best overall response (BOR) is determined by the highest qualitative value assessed during the study given a hierarchy of overall response results: iCR > iPR > iSD > iUPD > iCPD > NE. Note that even though iUPD is presented before iCPD in iRECIST hierarchy, in case iCPD occurs, it always overwrites iUPD for BOR derivation. A BOR of iCR or iPR requires confirmation of response at least 28 days after the date of the initial response in this non-randomized study (as per RECIST 1.1). BOR will be based on assessments collected after the treatment start date until confirmed disease progression (iCPD) or start of new anticancer therapy, whichever occurs earlier. BOR will be summarized descriptively by cohort/arm (including, Cohort 3: CyPep-1 5.0 mg/mL + Arm A: CyPep-1 5.0 mg/mL Monotherapy) for the SAF.

Secondary efficacy outcome is the objective response rate in all lesions (injected and non-injected) based on iRECIST. ORR will be defined as the percentage of subjects with a BOR of iCR or iPR. The ORR will be summarized by cohort/arm (including, Cohort 3: CyPep-1 5.0 mg/mL + Arm A: CyPep-1 5.0 mg/mL Monotherapy) including 95% 2-sided Clopper-Pearson CIs.

A waterfall plot of maximum percentage reduction from baseline in target lesion sum of diameters (mm) by best overall response will be provided for the SAF. A spider plot of percent change from baseline in target lesion sum of diameter measurements by best overall response will also be provided for the SAF. Only post-baseline data until an overall response of iCPD or start of new anticancer therapy will be included in the figures. In case a lesion is NE at a certain timepoint, sum of diameters will not be presented for that timepoint (in line with RECIST 1.1 recommendation).

A swimmer plot of iRECIST response assessment results will also be created for SAF.

Response evaluation data (including lesions measured, sum of diameters, iRECIST evaluation, maximum reduction in target lesion sum of diameters) will be listed for SAF. BOR and objective response will be listed for SAF.

